2. Determine whether prehospital tranexamic acid as compared to placebo results in a lower incidence of 24 hour mortality, acute lung injury, multiple organ failure, nosocomial infection, shock parameters, early resuscitation and transfusion needs, early seizures and pulmonary embolism.
3. To explore potential novel mechanisms by which tranexamic acid alters the inflammatory response to injury independent of effects on hyperfibrinolysis including effects on platelet and leukocyte activation via flow cytometry, measurements of plasmin levels and subsequent plasmin mediated complement activation and the early inflammatory cytokine response to trauma.
4. Determine whether different dosing regimens of tranexamic acid upon arrival in the hospital are associated with improvements in hyperfibrinolysis, markers of coagulopathy, clinical outcomes, and the early inflammatory response.

Pre Trial Start Period: The PIs and Site investigators will obtain FDA approval followed by approval for exception from consent for emergency research from their respective IRBs. The University of Pittsburgh as coordinating center will create a web based data entry platform for the trial.

Year 1: Following a 1 month training period for participating centers on enrollment procedures and TEG analysis, trial enrollment will begin with an estimated 330 patients enrolled by years end. Blood samples will be batched for plate assay analysis at the University of Pittsburgh and prospective outcomes data will be obtained,

entered and integrity verified. First interim analysis will occur at 1/3 of total patient enrollment. Those exploratory aim measurements that require fresh blood samples will occur at the University of Pittsburgh alone.

Year 2: An estimated additional 330 patients will be enrolled (total=660) by end of the second year and blood samples will again be batch analyzed for plate assay analysis. Continued prospective data collection and integrity verification for clinical outcomes will occur. A second interim analysis will occur after 2/3 of total patient enrollment. Exploratory aim measurements which require fresh blood samples will occur at the University of Pittsburgh alone.

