patients and across enrolling sites. To minimize important differences for the early pre-hospital management of each patient, scene time, referral hospital time and definitive transport times for emergency medical services will be obtained, recorded and monitored including pre-hospital interventions.

H.8. In-hospital Standard Operating Procedures: We have selected level I, academic, trauma centers with busy emergency medical transport services that are recognized for providing high level care of the injured patient. As the intervention begins in the pre-hospital setting, there exists the potential for in-hospital management differences to occur across centers as in any multi-center study which does increase the study results applicability. However, to minimize those differences where high level evidence exists for the early in-hospital management of each patient, and throughout a patients' admission, SOPs for resuscitation and transfusion will be employed over the initial 24 hours and throughout a patients' admission. SOPs for patients who are at risk of massive transfusion will target an FFP:PRBC ratio of at least 1:2 based upon currently available data. Once 48 hours has passed without ongoing blood transfusion requirements, standard transfusion practice evidence in the ICU will be followed including standard restrictive transfusion guidelines for each respective institution in line with the TRICC trial recommendations (transfusion trigger of hgb- 7.0).⁸⁹

I. Outcome Variables/Definitions

I.1. Primary Outcome: The primary outcome which will be utilized to power the study will be 30 day mortality. We anticipate that this study will be conducted with an exception from consent for emergency research and will require FDA approval. We will power the study using 30-day mortality as the primary outcome variable.

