I.2 Secondary Clinical Outcomes: Secondary clinical outcomes will include the incidence of hyperfibrinolysis (EPL > 7.5% by rapid-TEG analysis) upon arrival to the trauma bay within the first 6 hours, the incidence of acute traumatic coagulopathy (INR > 1.4), 24 hour mortality, acute lung injury, multiple organ failure, the development of nosocomial infection, early (24hr) seizures, in-hospital pulmonary embolism, presenting base deficit, 24 hour crystalloid requirements and 6 hour and 24 hour blood and blood component transfusion requirements (PRBC, FFP and platelets). *These same clinical outcomes will similarly be used for the randomized tranexamic acid dosage regimen comparison.*

I.3. Secondary Laboratory/Mechanistic Outcomes: All laboratory/mechanistic outcomes will be measured during the first 6 hours from trauma center arrival and at 12 and 24 hours (+/- 12 hours) out from injury. Those laboratory/mechanistic outcomes including flow cytometry which require fresh blood samples will be performed only at the University of Pittsburgh on a subset of patient samples unless participating centers have specific capabilities and following appropriate training for standardization. *These same laboratory/mechanistic outcomes will similarly be used for the randomized tranexamic acid dosage regimen comparison at 12 and 24 hours post-injury.*

I.4. Clinical Outcomes Methods/Definitions: All clinical outcomes will be prospectively evaluated for throughout ICU and hospital admission and the timing from the day of initial injury will be recorded for time-to-event statistical analysis.

I.4.1. 30 day and 24 hour mortality: 30 day mortality will be prospectively recorded from the day of trauma bay arrival. Over the first 24 hours we will document and record the time of death in hours. We suspect that patients enrolled will have a significant percentage of mortality that occurs in the first 24hrs.

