J.7. Missing Data: For 30-day mortality, given the transient nature of many of the subjects, extensive efforts will be made to ascertain vital status (see N.6.). Batch searches of the mortality databases will continue every quarter for subjects with unknown status, until trial closeout. For interim and final analyses, subjects who have not been reported as deceased by day 30 following ED admission from any of these sources we will use multiple imputation for the final value. As sensitivity analyses we will report the data with and without imputation. We will also report an analysis consistent with that used in other studies counting those missing as alive on day 30.

K. Sample Size Justification and Power Analysis:

We have determined the sample size for this proposal and powered the analysis based upon the primary outcome, 30 day mortality.

K.1. Primary Outcome 30 day mortality: Assuming a baseline mortality risk of 16% as was demonstrated in the Crash-2 study^{41,43} with 30 day mortality as the primary outcome, using a two-sided Z test with pooled variance and a 2 sided alpha of 0.05 the study will have a 90% power to detect a 7% or greater difference in 30

day mortality. The study will have 80% power to detect a 6% or greater difference in 30 day mortality. Using this power analysis, **497 patients in each arm, 994 total patients will be required, with a power of 0.85 and 2 sided alpha of 0.05. This will require on average each center to enroll 80 patients per year or 1 to 2 per week.** As busy, level 1 trauma centers with robust emergency medical programs were screened using the proposed inclusion criteria over 2012 data and selected for participation based upon this information, this sample size estimate is appropriate and attainable.

Power	Sample Size Grp 1 N1	Sample Size Grp 2 N2	Prop H1 Grp 1 or Trtmnt P1	Prop Grp 2 or Control P2	Diff if H0 D0	Diff if H1 D1	Target Alpha	Actual Alpha	Beta
0.9000	497	497	0.0919	0.1600	0.0000	-0.0681	0.0500		0.1000
0.8500	497	497	0.0965	0.1600	0.0000	-0.0635	0.0500		0.1500
0.8000	497	497	0.1003	0.1600	0.0000	-0.0597	0.0500		0.2000

L. Human Subjects:

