A summary report of the DSMB's findings will be submitted to regulatory agencies. At least one specialized clinician from the Data Safety Monitoring committee will be responsible for monitoring data safety. All related unanticipated problems will be directly handled by study's PIs and reported accordingly. We will also follow Department Of Defense Unique requirements documentation. The University of Pittsburgh and each participating center will have an AE logbook to record and to assure adequate attention for continuous assessment, analysis, and reporting of adverse effects using a standardized report form. The coordinating center will be responsible for all oversight of these risk assessments with monthly evaluations.

P.4. Interim Analyses: In concert with the DSMB, prior to initiation of the trial, the final monitoring plan will be developed to serve as the guide to the DSMB's decision-making process concerning early stopping of the trial. We will recommend interim analyses as 1/3 and 2/3 of patient enrollment. In making the decision to recommend termination of the study, the DSMB shall be guided by several types of information: (i) a formal stopping rule based on the primary analysis (comparison of treatment groups on the in-hospital mortality and 24 hour blood transfusion requirements), (ii) information on safety outcomes by treatment group, (iii) consistency between results for primary and secondary outcomes, and (iv) consistency of treatment effects across subgroups. Formal interim analyses will be performed at 6 months and then annually throughout enrollment. The DSMB will use the results of implementing the stopping rule as a guideline in evaluating the evidence for treatment effects. In making a recommendation to terminate the study, the DSMB will also consider information on safety outcomes, as well as consistency of outcomes for secondary outcomes and consistency of outcomes within important subgroups as described previously. The group sequential method described by O'Brien and

Fleming will be used to develop stopping rules to limit the impact of repeated testing on the probability of a Type I error.⁹⁵

Based on our power analysis, sample sizes of 497 in interventional group and 497 in control group can achieve 80% power to detect a difference of 0.06 between the group proportions of 0.10 and 0.16 at a significance level (alpha) of 0.05 using a two-sided z-test.

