We have proposed two interim analyses in this trial. We have based our testing on group sequential design that dividing patient entry into a fixed number of equal-sized groups and provides ethical and practical ways to make decision to stop the trial or continue based on repeated significance tests of the accumulated data after each group is evaluated.

According to the above power calculation and following the group sequential method described by O’Brien and Fleming in developing stopping rules to limit the impact of repeated testing on the probability of a Type I error, we will have equally spaced looks at 33%, 67% and 100% of patient accruals. This is equal to 166, 332, and 497 subjects in each group at these three looks. The following table and graph provide in details information in relation to alpha spending functions to determine the test boundaries according to O’Brien-Fleming method.

Details when Spending = O'Brien-Fleming, N1 = 497, N2 =497, P1 = 0.10, P2 = 0.16

Look	Time	Lower Bndry	Upper Bndry	Nominal Alpha	Inc Alpha	Total Alpha	Inc Power	Total Power
1	0.33	-3.71030	3.71030	0.000207	0.000207	0.000207	0.018687	0.018687
2	0.67	-2.51142	2.51142	0.012025	0.011890	0.012097	0.399207	0.417894
3	1.00	-1.99302	1.99302	0.046259	0.037903	0.050000	0.382494	0.800388
Drift 2.82089								

Look: These are the sequence numbers of the interim tests.

Time: These are the time points at which the interim tests are conducted. This is also related to proportion of subject accruals

Lower and Upper Boundary: These are the test boundaries. If the computed value of the test statistic z is between these values, the trial should continue. Otherwise, the trial can be stopped.

[figure not shown]
Nominal Alpha: This is the value of alpha for these boundaries if they were used for a single, standalone test. Hence, this is the significance level that must be found for this look in a standard statistical package that does not adjust for multiple looks.

Inc Alpha: This is the amount of alpha that is *spent* by this interim test. It is close to, but not equal to, the value of alpha that would be achieved if only a single test was conducted. The difference is due to the correction that must be made for multiple tests.

Total Alpha: This is the total amount of alpha that is used up to and including the current test.

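### P.4 ties the formal stopping rule to two endpoints that are not the primary outcome, and sets calendar looks that conflict with its own two-interim plan

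*Combined protocol and SAP*

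**What the plan says.** **Endpoint.** P.4 lists what should guide the DSMB on early termination. Item (i) is "a formal stopping rule based on the primary analysis (comparison of treatment groups on the in-hospital mortality and 24 hour blood transfusion requirements". Section I.1 says instead: "The primary outcome which will be utilized to power the study will be 30 day mortality". J.1.1 and K.1 agree with I.1. Section I.2 lists among the secondary clinical outcomes "6 hour and 24 hour blood and blood component transfusion requirements (PRBC, FFP and platelets". Section I.4 defines 30-day and 24-hour mortality but not in-hospital mortality. Appendix 4 has almost the same sentence as P.4, with 30-day mortality in the parenthesis. The charter's paragraph on efficacy analyses also names 30-day mortality.

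**Timing.** The paragraph of P.4 that recommends looks at 1/3 and 2/3 of enrollment goes on: "Formal interim analyses will be performed at 6 months and then annually throughout enrollment". Further down, P.4 states "We have proposed two interim analyses in this trial" and gives the look sizes: "This is equal to 166, 332, and 497 subjects in each group at these three looks". The Statement of Work ("First interim analysis will occur at 1/3 of total patient enrollment", and a second at 2/3), Project Milestones, the charter and Appendix 4 all plan two interims. P.1 uses the 6-month-then-annual schedule for comparing adverse events between arms.

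**Boundaries.** P.4 and Appendix 4 print one identical table: O'Brien-Fleming spending, 497 per group, 0.10 versus 0.16, three looks.

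**The concern.** A formal stopping rule has to fix the endpoint, the number and timing of looks, and the boundary at each look. P.4 supplies boundaries for one endpoint and two interims, but its text names two other endpoints and a second schedule that calls its looks formal. A DSMB working from P.4 alone could apply the printed bounds to comparisons, or at times, for which the overall 0.05 was not calculated. At stake are the trial's type I error statement and the clarity of any recommendation to stop early.

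**Working it through.** **Inputs.** 497 per arm, rates 0.10 and 0.16, two-sided alpha 0.05, bounds 3.71030, 2.51142 and 1.99302, drift 2.82089 (P.4, repeated in Appendix 4). Baseline: "Assuming a baseline mortality risk of 16% as was demonstrated in the Crash-2 study" (K.1, for 30-day mortality). Enrollment lasts 33 months (Project Milestones). 994 patients in total (K.1).

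**1. Reproduce the plan's table.**
- Drift = 0.06 / √(variance of the difference). Pooled: 0.06 / √(2 × 0.13 × 0.87 / 497) = 2.812. Unpooled: 0.06 / √((0.10 × 0.90 + 0.16 × 0.84) / 497) = 2.824. The printed 2.82089 lies between them.
- O'Brien-Fleming-type spending at one-sided 0.025 per side, with t = 1/3, 2/3, 1, gives bounds 3.7103, 2.5114, 1.9930 by recursive integration. The alpha increments are 0.000207, 0.01189 and 0.03790, total 0.0500. Power at the printed drift is 0.800.

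The table is therefore correct for one binary endpoint with two interims and a final test. It does not name its endpoint. The control rate of 0.16 is K.1's baseline for 30-day mortality, which identifies it by inference. No boundary is given for a transfusion endpoint or for looks at other times.

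**2. P.4 endpoints at the interims, 30-day mortality at the final.** Simulation under the null with the printed bounds. Assumed correlations: 0.9 between the two mortality endpoints, and 0 to 0.8 between mortality and transfusion.

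| Rule at an interim | Type I error |
|---|---|
| Both endpoints must cross in the same direction | 4.6% to 4.8% |
| Either alone may stop the trial for benefit | 5.7% to 6.3% |

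**3. Calendar looks on 30-day mortality.** Assume uniform accrual over 33 months and complete 30-day follow-up, so patients available at month m = 994 × (m − 1)/33.
- Months 6, 18, 30: 994 × 5/33 = 151, 994 × 17/33 = 512, 994 × 29/33 = 874.
- Months 6, 12, 24 (the other reading of annual looks after month 6): 151, 331, 693.

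Held means that a printed bound is not relaxed before its planned fraction (3.710, 3.710, 2.511, then 1.993). In order means 3.710, 2.511, 1.993, then 1.993.

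| Calendar looks replace the planned ones | Held | In order |
|---|---|---|
| Months 6, 18, 30 | 4.7% | 6.6% |
| Months 6, 12, 24 | 5.0% | 7.6% |

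If the calendar looks are added to the two planned ones and the bounds are held, type I error is 5.1% for either schedule.

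**4. The document's own accrual projection.** The Statement of Work expects 330 patients by the end of year 1 and 660 by the end of year 2: 330/994 = 33% and 660/994 = 66%. Looks at years 1 and 2 would then nearly coincide with the planned ones, leaving month 6 as the extra look. With about 165 patients there (half of 330, assumed), type I error is 5.0% with bounds held and 7.7% with bounds used in order.

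**The case against.** The strongest reply is that the right rule is already in the documents. P.4 says that a final monitoring plan will be developed with the DSMB, and P.1 leaves the interim plan to the board. Appendix 4 and the charter, which the board works from, both use 30-day mortality and two interims. P.1 suggests that the calendar schedule was meant for adverse-event review. On this view P.4 holds one uncorrected paragraph. Much of that stands, and it limits the effect. It does not remove the contradiction: P.4 is current protocol text, it calls its calendar looks formal, and nothing says that Appendix 4 supersedes it.

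Three stronger readings are tempting and are not supported.
- A reader might infer that P.4 contradicts a 30-day-mortality rule stated in the same section. P.4 never names 30-day mortality. Only the timing conflict is explicit inside P.4; the explicit endpoint conflict is with I.1, J.1.1, K.1, the charter and Appendix 4.
- A reader might infer that the trial's type I error is inflated. Every figure clearly above 5% needs a rule that no section states: stopping for benefit on either endpoint alone (P.4 joins them with 'and'), or using a printed bound before its planned fraction. The charter requires spent alpha to be recalculated if an interim is added. Doing so for the calendar looks would hold alpha at 0.05 and cost little power (about 0.795 if they replace the planned looks, 0.793 if they are added, against 0.800; looks placed by enrolled patients).
- A reader might count the differing review frequencies in P.1, the charter and Appendix 4 as a further error. They describe different activities and are left flexible, so choosing one is a preference.

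**Conclusion.** The concern holds as a contradiction in a stated decision rule. P.4 presents two endpoints as the primary analysis when neither is the primary outcome, and it gives two incompatible schedules for formal looks. The boundary table itself is correct for two interims and a final test of one binary endpoint at 0.10 versus 0.16. Read without misuse of the bounds, type I error is about 4.6% to 5.1%; under the unstated rules above it would be roughly 6% to 8%. These ranges rest on the assumed endpoint correlations and on uniform accrual, apart from the check against the projected yearly counts. Because the charter and Appendix 4 carry the 30-day version, the practical effect is limited. P.4 should still be corrected before the first look.

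**What to change.** 1. In P.4 item (i), replace the parenthesis with the one in Appendix 4's matching sentence, so that the rule compares treatment groups on 30-day mortality. Transfusion is then weighed under item (iii), consistency between primary and secondary outcomes.
2. Replace the calendar sentence in P.4 with wording such as: *Periodic DSMB safety reviews, including adverse events by arm, carry no formal efficacy test. The only formal efficacy interim analyses are the two at 1/3 and 2/3 of accrual (166 and 332 per group) with 30-day follow-up complete; any added formal efficacy interim analysis requires alpha to be recalculated.* The last clause is limited to efficacy interims so that it does not catch the by-arm adverse-event reviews expected under P.1.
3. Appendix 4 triggers the looks by a share of expected primary events, while glossing this as about a month after 1/3 and 2/3 accrual. Make that trigger agree with the accrual-based one.

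**Cost.** Wording only: boundaries, sample size and data collection do not change. The DSMB gives up transfusion as a formal stopping criterion and any formal efficacy test at calendar reviews.

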Proposed Community Consultation and Public Disclosure Plan STAAMP Trial

- I. Community Consultation
 - A. City of Pittsburgh
 1. Consultation with representatives of the communities in which the clinical investigation will be conducted and from which the subjects will be drawn
 - B. Website

Information about the current STAAMP Trial will be posted on a website which has been developed for this purpose. Contact information will be provided for questions and comments. All multimedia material will have the following website listed: www.acutecareresearch.org

There will be information on how to get more information about the trial and how to obtain on “opt out bracelet” if desired.
 - C. Surveys

Paper surveys will be placed in the Trauma Service outpatient clinic. They will also include the web address and contact information. A detailed telemarketing survey will be performed over a four-week period with approximately 500 households in the zip codes we intend to conduct this study.
 - D. Presentation to Pennsylvania Emergency Health Services Counsel

We will schedule to present at one of their meetings
- II. Public disclosure
 - A. Multi-Media

The UPMC Media Office will issue a press release describing the upcoming study and locations of public forums.
 - B. Notifications will be posted on our local Pittsburgh Authority public transportation buses. The website address will be posted. Contact information will be provided for questions and comments. This will

include information regarding how to obtain an opt-out bracelet. This has been the most effective means of getting feedback in our area.

C. Flyers

We will distribute flyers directing traffic to our local website. Flyers will be provided in hospital waiting areas and community bulletin boards.

D. Presentation to local paramedics, emergency physicians, and medical directors

E. E-mail listserv

We will create an e-mail listserv using Campaign Monitor and will add community members that express interest in our research based on e-mails, calls, inquiries, and referrals.

F. Opt out bracelets will be made available upon request. They will be orange and state "NO STAAMP".

**Clinical Protocol Appendix 3 – Data Safety Monitoring Board (DSMB) Charter
DSMB Charter**

Study of Tranexamic acid during Air and ground Medical Prehospital transport (STAAMP) trial

August 03, 2017

Version 1.3

Data Safety Monitoring Board (DSMB) Overview

Trial Description and Study Design

- Trial name: Study of Tranexamic acid during Air and ground Medical Prehospital transport (STAAMP) trial
- Principal investigator (PI): [name], MPH
- Funding agency: Department of Defense
- Trial design: Multi-center, prospective, randomized, blinded, controlled interventional trial.
- Phase: III
- Number of patients: 994
- Number of sites: 4

DSMB Description

- This DSMB will be coordinated by the PI, [name], MPH.
- This DSMB will be independent of the investigators, funding agency, regulatory agencies, and institutional review boards.
- This charter will be approved by its DSMB members as attested to by signature of the chairperson.

DSMB Membership

- Members will disclose conflicts of interest and will be cleared of significant conflicts of interest and potential conflicts of interest in accordance with provisions in this charter.
- DSMB members will sign confidentiality agreements covering DSMB activities.
- Composition of membership will be researchers with the following expertise: hematology (transfusion medicine), surgery (trauma/critical care), prehospital emergency medicine, epidemiology (clinical trial design), and biostatistician.
- Remuneration will be provided any expenses related to DSMB activities.

Reporting

- Unblinded data to be reviewed by the DSMB will be provided by an independent statistician. Issues and recommendations identified by the DSMB will be provided to the principal investigator by the DSMB chairperson in accordance with this charter.
- Details of closed session deliberations (e.g., minutes) will be considered privileged and not subject to disclosure except as required by law.

Introduction

The purpose of this charter is to define the roles and responsibilities of the DSMB, delineate qualifications of the membership, describe the purpose and timing of meetings, provide the procedures for ensuring confidentiality and proper communication, and outline the content of the reports.

The DSMB will function in accordance with the principles of the following documents: FDA document "Guidance for Clinical Trial Sponsors: On the Establishment and Operation of Clinical Trial Data Monitoring Committees".

Study Overview/Summary

Objective/Hypothesis: The primary hypothesis will be that prehospital infusion of tranexamic acid in patients at risk for bleeding will reduce the incidence of 30 day mortality. The secondary hypotheses include that prehospital tranexamic acid will reduce the incidence of hyperfibrinolysis, acute lung injury, multiple organ failure, nosocomial infection, mortality, early seizures, pulmonary embolism and early resuscitation needs, reduce or prevent the early coagulopathy as demonstrated by improving presenting INR and rapid thromboelastography parameters, reduce the early inflammatory response, plasmin levels, leukocyte, platelet and complement activation, and determine the optimal dosing of tranexamic acid post-injury..

Specific Aims:

Aim#1: Determine whether prehospital tranexamic acid as compared to placebo results in a lower incidence of 30 day mortality, 24 hour mortality, acute lung injury, multiple organ failure, nosocomial infection and improved shock parameters and early resuscitation and transfusion requirements.

Aim#2: Determine whether prehospital tranexamic acid as compared to placebo reduces hyperfibrinolysis, lowers the incidence of acute traumatic coagulopathy and improves early markers of coagulopathy.

Aim#3: To explore novel mechanisms by which prehospital tranexamic acid alters the inflammatory response independent of effects on hyperfibrinolysis including analysis of platelet and leukocyte activation, plasmin levels and plasmin mediated complement activation and the early cytokine response to trauma.

Aim#4: Determine whether different dosing regimens of tranexamic acid upon arrival in the hospital are associated with improvements in hyperfibrinolysis, coagulopathy, clinical outcomes and the early inflammatory response.

Study Design: Multi-center, prospective, randomized, blinded, controlled interventional trial over 3 years focusing on patients with concern for bleeding who are transported via air medical transport to definitive care.

Population: Blunt or penetrating injured patients transported via emergency medical transport within two hours of injury with concern for bleeding with 1.) a documented systolic blood pressure < 90 mmHg en route at outside/referral facility AND 2.) documented tachycardia (> 110 bpm) en route or at outside/referral facility..

Inclusion Criteria:

1. Blunt or penetrating injured patients being transported via emergency medical services from the scene of injury or from referring hospital to a definitive trauma center that is participating in the trial

AND

2. Within 2 hours of time of injury

AND

3A. Hypotension (Systolic Blood Pressure (SBP) < 90mmHg)

i. At scene of injury or during emergency medical transport

ii. Documented at referring hospital prior to emergency medical transport arrival

OR

3B. Tachycardia (heart rate >110 beats per minute)

i. At scene of injury or during emergency medical transport

ii. Documented at referring hospital prior to emergency medical transport arrival

Inclusion criteria #3. and #4. not required to be simultaneous

Exclusion Criteria:

1. Age > 90 or < 18 years of age;

2. Inability to obtain intravenous or intraosseous access ;

3. Documented cervical cord injury with motor deficit;

4. Known prisoner;

5. Known pregnancy;

6. Traumatic arrest with > 5 minutes CPR without return of vital signs;

7. Penetrating cranial injury

8. Traumatic brain injury with brain matter exposed;

9. Isolated drowning or hanging victims

10. Wearing an opt out bracelet.

11. Isolated fall from standing

12. Objection by patient or family member

Interventional Arm: The Intervention will have both a prehospital phase and in-hospital phase. Investigational Drug Services (IDS) at the University of Pittsburgh will be utilized to supply and organize both tranexamic acid and placebo along with respective normal saline bolus and infusion bags to all participating trial sites. IDS at the University of Pittsburgh has a long track record of managing large multicenter trials and is currently executing and responsible for over 150 inpatient and outpatient clinical trials.

Prehospital Phase Intervention: Once inclusion and exclusion are verified while the patient is being transported via emergency medical transport to a STAAMP trial participating center, in a randomized, double blinded fashion, either 1 gram bolus of tranexamic acid diluted in 100cc of normal saline (preprepared on helicopter) or placebo of identical volume will be infused into the patient over approximately 10 minutes. After receiving the prehospital phase intervention, standard operating procedures utilizing goal directed crystalloid infusion will be followed

In-hospital Phase Intervention: Upon arrival, patient blood and labs will be sampled and arrival rapid-TEG analysis will be performed within first 60 minutes. After inclusion and exclusion criteria verification by research staff, in a double blinded, randomized fashion, those patients who received tranexamic acid in the prehospital phase will receive 1 of 3 different dosage regimens:

1. *Standard Tranexamic acid Dosing:* 1 gram infusion over 8 hours

2. *Repeat Tranexamic acid Dosing:* 1 gram bolus and 1 gram infusion over 8 hours
3. *Abbreviated Tranexamic acid Dosing:* No further tranexamic acid to be given

For intervention blinding purposes, each patient will receive both a bolus dose (either tranexamic acid or placebo) and 8 hour infusion (either tranexamic acid or placebo) depending on the randomized dosing regimen.

Placebo/Control Arm: Prehospital phase patients randomized to placebo will receive identical placebo diluted in 100cc of normal saline and infused over 10 minutes. Patients who received prehospital phase placebo will receive in-hospital identical placebo bolus and 8 hour placebo infusion for blinding purposes

Randomization: The randomization scheme will have both a prehospital phase and in-hospital phase.

Prehospital Phase Randomization: Individual patients meeting criteria while en route via emergency medial transport will be randomized using an allocation sequence block size of 8 to either 1 gram of tranexamic acid or placebo diluted in 100cc of normal saline given over 10 minutes. A single prehospital treatment box containing ascending numerically labeled (1-8) treatment packs (randomized with a computer random number generator) will be on board each respective emergency transport vehicle. In an ascending numerical order fashion treatment packs will be utilized for enrolled patients. The box and treatment pack # will be recorded by research staff upon arrival for all randomized patients. The patient and all treatment and research staff will be blinded to the treatment arm. All intervention vials will be covered to obscure view of vial contents to prehospital staff giving the intervention and amber colored syringes will be utilized to maintain blinding. IDS at the University of Pittsburgh will be unblinded to the prehospital intervention. Additionally, the pharmacy at each respective participating center will have access to the prehospital randomization/assignment scheme once the prehospital intervention box and treatment # are provided to them by the accepting research staff at each participating center.

In-hospital Phase Allocation: Using a web based, randomization assignment program built specifically for the trial, research staff will provide and input the prehospital intervention box # and treatment pack # into the web based platform at each site and be provided the In-hospital treatment allocation to be utilized for the second phase intervention. IDS at the University of Pittsburgh and each respective pharmacy at the participating sites will be provided with the random allocation sequence and will be unblinded to the in-hospital allocation assignment. The accepting research staff and pharmacy will verify they have the same in-hospital phase treatment assignment as an additional check to the allocation assignment. An allocation sequence based upon a block size of 9 again generated with a computer random number generator will be utilized for those who received prehospital Tranexamic Acid. Each respective IDS or pharmacy will prepare the inhospital phase treatment (10 minute and 8 hour infusion). The patient and all treatment and research staff will be blinded to the treatment that is received.

Blinding: The trial is a double blinded trial for both the prehospital phase and in-hospital phase interventions. The participants, investigators, research coordinators and staff, and persons having any contact with the patients will be blinded to study treatment assignments. The IDS at the University of Pittsburgh will be unblinded to the prehospital phase treatment arm and the respective pharmacy at each center will be unblinded once the treatment prehospital treatment information is

provided to them by research staff. Both IDS at the University of Pittsburgh and the respective IDS or pharmacy at each center will be unblinded to the in hospital treatment assignment.

Roles and Responsibilities

DSMB Roles and Responsibilities

This DSMB will

- Meet periodically (see DSMB Meetings) to review aggregate and individual subject data related to safety, data integrity and overall conduct of the trial.
- Review specific interim analyses for efficacy (see Study Review Criteria/Stopping Rules and Guidelines).
- Provide recommendations to continue or terminate the trial depending upon these analyses.
- Communicate other recommendations or concerns as appropriate.
- Operate according to the procedures described in this charter and all procedures of the DSMB.
- Follow conflict of interest guidelines as detailed below (see DSMB Membership).
- Comply with confidentiality procedures as described below (see Confidentiality).
- Maintain documentation and records of all activities as described below (see DSMB Meetings, DSMB Reports).

Principal Investigator (or Designees) Roles and Responsibilities

The PI will directly or through delegation:

- Assure the proper conduct of the study.
- Assure collection of accurate and timely data (monitoring and data management).
- The PI will designate an independent statistician to compile and report SAEs to the DSMB.
- Promptly report potential safety concern(s) to the DSMB.
- Prepare summary reports of relevant data for the DSMB. (This may include analyses not otherwise outlined in this charter based upon findings.)
- Provide an independent facilitator for presentation of results during DSMB meetings if requested by the DSMB.
- Communicate with regulatory authorities, IRB, and investigators, in a manner that maintains integrity of the data, as necessary. (This communication is not the responsibility of the DSMB.)
- Provide funding for the study and DSMB.
- PI will not attend the closed session of the DSMB Meeting.

DSMB Membership

The DSMB will consist of at least 4 members. The DSMB members have been selected by the PI in consultation with the investigators.

As characteristic qualifications, members will:

- Work professionally and meet qualifications for their respective professions.
- Comply with accepted practices of their respective professions.
- Comply with the conflict of interest policies specified by the standard operating procedures (SOPs) of the PI to ensure that members do not have serious scientific, financial, personal, or other conflicts of interest related to the conduct, outcome, or impact of the study according to

the guidelines specified below (e.g., engaged in any simultaneously occurring competitive trials in any role that could pose a conflict of interest for this study).

- Be independent from the PI, IRB, regulatory agencies, principal investigator, co-principal or sub-principal investigator, site investigator, site sub-investigator, clinical care of the study subjects, or any other capacity related to trial operations.
- Not be on the list of Notice of Initiation of Disqualification Proceedings and Opportunity to Explain (NIDPOE) (<http://www.fda.gov/foi/nidpoe/default.html>) and/or debarred list of investigators (http://www.fda.gov/ora/compliance_ref/debar).

Although each DSMB member will be expected to serve for the duration of the trial, in the unlikely event that a member is unable to continue participation, the reason will be documented and a replacement will be selected by the PI.

The DSMB will follow conflict of interest guidelines referenced by the Department of Health and Human Services, Financial Relationships and Interests in Research Involving Human Subjects: Guidance for Human Subject Protection (<http://www.hhs.gov/ohrp/humansubjects/finreltnn/fguid.pdf>). DSMB members will sign a non-conflict of interest statement in regard to this study which will be on file with the PI. As determined by the PI, conflicts of interest and/or potential conflicts of interest (as determined by SOPs) will be reduced to the greatest extent that is consistent with assembling a highly competent DSMB. Any questions or concerns that arise regarding conflicts of interest will be addressed by the DSMB chairperson with input from other DSMB members and PI as necessary.

DSMB Meetings

Projected Schedule of Meetings

